### **Statistical Analysis**

1. Content of statistical analysis: a. Dropout sample: the accuracy numbers lost and dropout rate of subjects are described, and reasons for the dropout is given. b. Balance comparison: The

comparability of subjects in two groups are compared via the baseline information assessing. c. Efficacy analysis: we will treat the QoR-40 as the primary outcome to evaluate the efficacy of TEAS treatment in improving the postoperative recovery after total knee arthroplastic, a mean and deviation as the expression of primary outcome and compared between groups using one-way ANOVA (SNK method), however, before statistic performed, a test of normal distribution of data should be used to determine whether the data are suitable for analysis using the one-way ANOVA. Additional four composite outcome measures (incidence of any postoperative complication, length of hospital stay, level of stress response, level of inflammatory response) are also used as secondary outcomes to determine the efficacy of

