### **Outcome Measures**

Primary outcome measure: The primary outcome is the Quality of Recovery-40 questionnaire (QoR-40). It was specifically designed to evaluate quality of recovery in subject after surgery with including five aspects: emotional state, physical comfort, psychological support, physical independence and pain. There are 40 items in total, each adding 1-5 points to the score. Thus, the highest possible score is 200 points; higher scores indicate better quality of recovery. The QoR-40 will be evaluated at preoperative day 1 and postoperative day 1, 3, 7, respectively.

Secondary outcome measures: a. Incidence of postoperative complications: we will assess incidence of postoperative complications when initially find by participant or accompanying family members and diagnosed through examination or scale. Any complication after surgery will be recorded and filled in the case report form. When subject send back to ward, we will require the accompanying family members to record any complaint from subject. Assessment of incidence of postoperative complications will be going on three times and occur at postoperative day 1, 3, 7, respectively. b. The length of hospital stay (LOH): The LOH = the day of patient discharge from hospital – the day of patient admit to hospital, which is calculated base on the Hospital Information System. c. Level of stress response: The Adrenocorticotropic Hormone (ACTH), Cortisol (COR) are chosen to address the level of perioperative stress response. Blood sample taken intravenously and collected at the time of 1 day before surgery (baseline) and 1st day, 3rd day after surgery, respectively. d. Level of inflammatory response: In clinic, the C Reactive Protein and Neutrophil-lymphocyte ratio are well-known to represent the level of perioperative inflammatory response [27, 28]. Blood sample taken intravenously and collected at the time of 1 day before surgery (baseline) and 1st day, 3rd day after surgery, respectively.

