### Sample Size Calculation

This trail contains two groups. A sample size estimation formula can be used to calculate the numbers of subjects in each group, base on two-groups, randomly, controlled design.

$$n = \frac{(Z_{1-\alpha} + Z_{1-\beta})^2 \cdot (\sigma_1^2 + \sigma_2^2)}{\delta^2}$$

where  $n$ ,  $\sigma$ ,  $\delta$  represent the sample size in each group, standard deviation, mean difference of two groups, respectively. In a condition of  $\alpha = 0.05$ ,  $\beta = 0.1$  with a two sided test, we obtain  $Z_{1-\alpha} = 1.96$  and  $Z_{1-\beta} = 1.282$ . According to previous data by Bai et al, the primary outcome of QoR-40

in the article is  $176.9 \pm 11.1$  vs.  $164.3 \pm 13.7$  as compare experimental group to control group ( $p = 0.006$ ), the sample size for each group was 21 cases and the final sample size estimated in each group was 26 cases with adding a 20% dropout rate. Totally 54 subjects are needed.

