### **Intervention**

Surgical day, the subject will be transferred into operation room and calms down for few minutes with a supine position lying on the surgical bed. Acupoint stimulation administered at 30 min before epidural administration and 30 min after wound closed 2/10 HZ and the intensity adjust to maximal tolerance by participant until end of treatment. The acupuncture points are selected on

the basis of WHO Standard International Acupuncture Nomenclature, and zusanli (ST36, downward 3 inches to the hollow of patellar ligament lateral, Fig.2 a), sanyinjiao (SP6, 3 inches above the top of malleolus medialis, Fig.2 b), neiguan (PC6, 2 inches to the midpoint of wrist skin crease, Fig.2 c), quchi (LI11, the lateral end of the elbow crease when elbow flex 90 degree, Fig.2 d) are located specifically as figure.2 shown. After acupoint area disinfected by 75% alcohol, a medical electrode will be placed on the acupuncture points and connecting to an electro-acupuncture stimulator (SDZ-V, Suzhou medical technology Co. Ltd., Suzhou, China).

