### **Study protocol**

All participants will fill a demographic information sheet (including age, gender, height, weight, ASA classification status, education level, income, previous anesthesia experience/complications, medical history, anxiety and depression, preoperative examination and based line functional ability). The first assessment of patient status will take place at 1 day before surgery (baseline), and repeat at 1st day, 3rd day, 7th day after surgery.

**Safety Assessment:** We will define an adverse event as an event if more than three subjects suffer a same symptom, such as local skin rash, dizziness, and low blood sugar during the treatment-evaluation period. These events will be statistically analyzed, and treatment safety is evaluated in accordance with the research protocol. If serious adverse events occur, we will report it immediately and take actions accordingly.

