### **Methods of Statistical Analysis**

According to the principle of intention-to-treat (ITT), our data will contain all subjects enrolled. Efficacy and safety measures will be analyzed in accordance with protocol strictly, thus, only subjects who completed the entire trial and followed the protocol requirements should be analyzed. Quantitative and qualitative variables are described statistically with  $X \pm SD$  and count numbers, separately. Quantitative variables will be analyzed by one-way ANOVA (SNK method) in statistic, a normal data distribution needed before performance. Qualitative variables will be analyzed using either  $\chi^2$  test or Fisher' s exact test. All statistical tests are two-sided, and P value  $< 0.05$  will be considered to be statistically significant. Statistical analysis will be performed using SPSS 17.0 software for application.

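### The planned one-way ANOVA ignores the preoperative QoR-40 and blood-marker values; ANCOVA would use them at almost no cost

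*Combined protocol and SAP*

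**What the plan says.** All five quantitative measures at issue have a value from before treatment. For the primary outcome, Outcome Measures states: "The QoR-40 will be evaluated at preoperative day 1 and postoperative day 1, 3, 7, respectively". For ACTH, cortisol, C-reactive protein (CRP) and neutrophil-lymphocyte ratio (NLR), the same section has blood "collected at the time of 1 day before surgery (baseline) and 1st day, 3rd day after surgery, respectively". The Study protocol section agrees on the timing: "The first assessment of patient status will take place at 1 day before surgery (baseline"). Stimulation comes later, on the day of surgery: "Acupoint stimulation administered at 30 min before epidural administration and 30 min after wound closed".

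The analysis does not use these values to estimate the treatment effect. Statistical Analysis expresses QoR-40 as "a mean and deviation as the expression of primary outcome and compared between groups using one-way ANOVA (SNK method"), and Methods of Statistical Analysis generalises this: "Quantitative variables will be analyzed by one-way ANOVA (SNK method) in statistic". No covariate, change score or repeated-measures model is named. The one stated use of baseline is a balance check, in which "comparability of subjects in two groups are compared via the baseline information assessing".

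On size, the Sample Size Calculation section arrives at 21 per group, and then "the final sample size estimated in each group was 26 cases with adding a 20% dropout rate".

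**The concern.** A value taken before stimulation cannot have been affected by it, so each preoperative measurement is a legitimate covariate. If it predicts the postoperative value, one-way ANOVA leaves that predictable between-patient variation in the error term. The group comparison stays unbiased and keeps its error rate, but its confidence intervals are wider and its power lower than the scheduled data allow.

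With about 21 evaluable patients per group and QoR-40 as the primary outcome, this could matter. The sample size was set for 90% power in a two-group comparison, while the trial randomises experimental (E), placebo (P) and control (C) groups and compares them by the Student-Newman-Keuls (SNK) procedure.

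**Working it through.** **Inputs from the documents.** Sample Size Calculation: QoR-40 176.9 (SD 11.1) against 164.3 (SD 13.7), a difference of 12.6; two-sided alpha 0.05; beta 0.1; 21 per group, 26 with dropout. Randomization: three equal groups.

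**Assumed, because the documents are silent.** The baseline-to-follow-up correlation r (0 to 0.7); P's mean (equal to C, or midway at 6.3 points above it); a common SD; bivariate normal data.

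**The plan's own figure.** n = (1.96 + 1.282)² × (11.1² + 13.7²) / 12.6² = 10.51 × 310.90 / 158.76 = 20.58, rounded up to 21. Then 21 × 1.2 = 25.2, rounded up to 26. Both reproduce. Baseline plays no part in the formula.

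**Gain from the covariate.** Common variance = 310.90 / 2 = 155.45, so SD = 12.47. ANCOVA leaves a residual variance of (1 − r²) × 155.45. Ignoring the lost degree of freedom, 21 per group with ANCOVA is worth 21 / (1 − r²) without it:

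| r | Variance removed | Equivalent unadjusted n |
|---|---|---|
| 0.2 | 4% | 21 / 0.96 = 21.9 |
| 0.3 | 9% | 21 / 0.91 = 23.1 |
| 0.5 | 25% | 21 / 0.75 = 28.0 |
| 0.7 | 49% | 21 / 0.51 = 41.2 |

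**Cost of the covariate.** Estimating the slope inflates the variance of a contrast by about 1 + 1/(3n − 5). At n = 21 this is 1 + 1/58 = 1.017. Break-even is where (1 − r²) × 1.017 = 1, that is r = √(1/59) = 0.13. At 18 and 26 per arm break-even is 0.14 and 0.12.

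**Three-arm simulation** (60,000 trials per cell). Plan: SNK, testing the range of three means first and then adjacent pairs, on 3n − 3 error degrees of freedom. Alternative: ANCOVA group F test at 0.05, then pairwise t tests at 0.05, on 3n − 4. Power (%) for E against C:

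| Per arm | P's mean | SNK | ANCOVA, r = 0 | 0.2 | 0.3 | 0.5 | 0.7 |
|---|---|---|---|---|---|---|---|
| 21 | equal to C | 86.1–86.8 | 86.5 | 88.0 | 89.9 | 94.9 | 99.3 |
| 21 | midway | 81.3–81.7 | 81.0 | 82.4 | 84.7 | 91.2 | 98.3 |
| 26 | equal to C | 93.3–93.4 | 93.5 | 94.4 | 95.5 | 98.2 | 99.9 |
| 26 | midway | 89.9–90.0 | 89.4 | 90.8 | 92.2 | 96.4 | 99.6 |

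SNK power does not depend on r; the ranges are simulation noise. The 26-per-arm rows assume no dropout.

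Mean 95% CI half-width for E-C, in points, at the same values of r:

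- 21 per arm: 7.66 unadjusted; 7.73, 7.58, 7.37, 6.69, 5.52 with ANCOVA.
- 26 per arm: 6.87 unadjusted; 6.91, 6.77, 6.60, 5.99, 4.94 with ANCOVA.

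**Checks.**

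- Two groups of 21, as in the plan's formula: t test 89.2%; ANCOVA 88.4, 89.6, 91.2, 95.2, 99.3%.
- Unequal SDs (E 11.1, P and C 13.7), 21 per arm, P equal to C: SNK 84.8%; ANCOVA 84.9, 86.5, 88.3, 94.1, 99.1%.
- E against P at an assumed 6.3 points, 21 per arm: SNK 35%; ANCOVA 35.1, 36.2, 37.9, 45.2, 60.6%.
- Familywise error with all means equal (14, 21 or 26 per arm; r = 0 or 0.5): SNK 4.8–5.0%, ANCOVA 4.7–5.1%. False P-C rejection when only E differs: SNK 4.7–5.1%, ANCOVA 4.9–5.1%.

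**The case against.** The strongest reply is that nothing here is wrong. The planned test is valid and conventional, and exchanging one valid analysis for a more efficient one may be called preference. The benefit also rests on a correlation that appears nowhere in the documents. With P midway and r = 0.2, power at 21 per arm moves by about one point and the half-width only from 7.7 to 7.6. This stands as a limit on the size of the claim. It does not change the direction, because break-even is at r of about 0.13 and the downside is about one point.

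Three narrower objections also have substance:

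- **Blood markers.** No gain has been shown for them, and surgery may swamp their preoperative level. The case for adjusting them is low cost alone.
- **Two changes at once.** The alternative replaces SNK as well as adding a covariate. Pairwise t tests after an overall F test, without a covariate, give about 87.2% (21 per arm, P equal to C). The covariate alone therefore adds about −0.7, 0.8, 2.7, 7.7 and 12.1 points at r = 0, 0.2, 0.3, 0.5 and 0.7.
- **The stated total of 54.** Over three arms that is 54 / 3 = 18 each, and the power levels above are then optimistic. In 20,000 trials per cell, SNK gives 79–80% (P equal to C) or 74–75% (midway), and ANCOVA at r = 0.5 gives 91% or 86%. The gain is no smaller, but the mismatch between a two-group calculation and three randomised groups is a separate problem that adjustment neither solves nor excuses.

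Statistical Analysis also breaks off mid-sentence, but only after the primary analysis has been stated, and Methods of Statistical Analysis repeats the method for quantitative variables in general.

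**Conclusion.** The concern holds as a matter of efficiency, not of validity. The plan schedules a preoperative value for every one of these outcomes and then uses it only to check balance. For QoR-40 the gain is negligible below r of about 0.2, visible from about 0.3 and substantial at 0.5 or more.

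Against the plan's 90% target, SNK in three arms of 21 gives roughly 81–87% for E against C. ANCOVA reaches about 90% at r = 0.3 if P equals C, and exceeds 90% at r = 0.5 in both scenarios. These figures rest on the assumed r, the assumed mean for P, normal data (QoR-40 is capped at 200) and a single postoperative assessment; r may differ between days 1, 3 and 7.

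The change is recommended rather than essential. Confidence is medium because the size of the benefit cannot be settled from the documents.

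**What to change.** Before unblinding, amend the SAP for QoR-40, ACTH, cortisol, CRP and NLR:

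- At each postoperative assessment, replace one-way ANOVA with ANCOVA: group (E, P, C) as factor and the outcome's own preoperative value as covariate.
- Report adjusted E-C, E-P and P-C differences with 95% CIs.
- SNK does not carry over directly to adjusted means. Test the three contrasts at two-sided 0.05 only if the overall ANCOVA group F test is significant at 0.05. With exactly three groups this controls familywise error within an assessment.
- Apply the normality check that the plan already requires to the model residuals. Settle any log transformation of the markers in advance or from blinded data.

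The cost is wording and one degree of freedom per model; no new measurement is needed. If r is 0, the loss against SNK lies between nothing and 0.6 points at 21 or 26 per arm, and is about one point at most at 18 per arm. In clearly smaller groups it can reach about 2 points. The change does not settle which of days 1, 3 and 7 is primary; that needs its own decision.

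### The trial is sized for a single E vs C comparison at 1.96, but QoR-40 is analysed by all-pairs SNK over three arms with no named primary contrast or confidence interval, which costs roughly 3 to 8 points of power at 21 per arm

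*Combined protocol and SAP*

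**What the plan says.** **Sizing.** The Sample Size Calculation section opens with "This trail contains two groups" and takes its QoR-40 figures (176.9, SD 11.1, and 164.3, SD 13.7) "as compare experimental group to control group". It uses alpha 0.05 "with a two sided test", critical value 1.96 and beta 0.1, and reports that "the sample size for each group was 21 cases". It then states that "the final sample size estimated in each group was 26 cases with adding a 20% dropout rate" and that "Totally 54 subjects are needed".

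**Arms.** The Participants and Randomization sections allocate equally to three arms: E, P and C.

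**Analysis.** Item 1c of the Statistical Analysis section has QoR-40 "compared between groups using one-way ANOVA (SNK method", summarized by mean and deviation. The Methods of Statistical Analysis section repeats the choice: "Quantitative variables will be analyzed by one-way ANOVA (SNK method) in statistic". Tests are two-sided at 0.05. Neither section says which pair of arms carries the primary conclusion, or plans a difference with a confidence interval. The Outcome Measures section has QoR-40 assessed on postoperative days 1, 3 and 7, and no day is named as primary.

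**The concern.** The sample size and the analysis describe different tests. The first is one two-group comparison with a fixed critical value. The second is a step-down range test over three means, in which the hurdle for E vs C depends on where the P mean happens to fall. The sizing makes no allowance for this, so the 90% power it plans for is not the power of the planned analysis.

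SNK is also a stepwise test that sorts arms into homogeneous subsets and supplies no confidence interval. If E vs C were not significant, the planned output would not show which QoR-40 differences had been ruled out.

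**Working it through.** **1. Reproduce the plan's figure.** Difference = 176.9 - 164.3 = 12.6. Sum of variances = 11.1² + 13.7² = 123.21 + 187.69 = 310.90. So n = (1.96 + 1.282)² × 310.90 / 12.6² = 10.511 × 310.90 / 158.76 = 20.58, rounded up to 21. The stated figure is correct for a two-group test.

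**2. Critical values under SNK.** With three arms of 21, error df = 3 × 20 = 60.
- Widest of three means: q(0.95; 3, 60) = 3.399, and on the t scale 3.399/√2 = 2.403.
- Adjacent means, tested only if the widest range has passed: t(0.975; 60) = 2.000.

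**3. What this means in QoR-40 points.** Root-mean-square SD = √(310.90/2) = 12.47. Standard error of a difference = 12.47 × √(2/21) = 3.85. The observed E minus C difference needed is 2.000 × 3.85 = 7.7 points for a pre-specified contrast, and 2.403 × 3.85 = 9.2 points when the three-mean value applies.

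**4. Power of a fixed test at 21 per arm.** Non-centrality = 12.6/3.85 = 3.27. Power is 90.6% by the normal approximation and 89.2% by the two-group t-test. With the error pooled over three arms it is 89.7%. It would be 80.5% if E vs C were always judged at 2.403.

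**5. Power of the full step-down rule.** This depends on the mean and SD of P, which the documents do not give, so both are assumptions. The SNK rule was simulated with a true E minus C difference of 12.6 and SDs of 11.1 (E) and 13.7 (C). The comparator is the E vs C contrast from the same ANOVA at two-sided 0.05.

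| Evaluable per arm | P mean (assumed) | P SD (assumed) | SNK | Pre-specified contrast |
|---|---|---|---|---|
| 21 | equal to C | 13.7 | 85% | 88% |
| 21 | midway | 12.47 | 82% | 90% |
| 21 | equal to E | 11.1 | 88% | 91% |
| 18 | equal to C | 13.7 | 78% | 83% |
| 18 | midway | 12.47 | 75% | 85% |
| 18 | equal to E | 11.1 | 82% | 86% |

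At 21 per arm the loss is roughly 3 to 8 points. The P SD matters a little through the pooled error: with P midway and an SD of 13.7, SNK gives 80% against 88%.

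The 18-per-arm rows are 54/3, with no dropout. With 26 evaluable per arm, SNK gives 90-94%.

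**6. How often 2.40 applies.** At 21 per arm with a common SD of 12.47, E and C are the two extreme sample means in about 50% of trials if P equals C or E, about 79% if P is a quarter of the way from C to E, and about 90% if P is midway.

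**7. Price of keeping SNK.** Holding 90% power with E vs C always judged at the three-mean value needs 27 evaluable per arm, or 27/0.8 = 33.75, so 34, after 20% dropout.

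**The case against.** SNK is a legitimate all-pairs method. With three means at a single time point it holds the family-wise error at 5%, and it buys three tested comparisons with the power it gives up. The analysis text states no primary contrast. The Placebo group section gives P a stimulation while the Control group section gives C none, so E vs P may interest the sponsor as much as E vs C, and putting E vs C first could be called the reviewer's preference. The loss is also moderate, and with all 26 per arm evaluable SNK reaches 90% or more.

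Much of this stands. SNK is not invalid here, and the point is not about inflated error. But E vs C is the only contrast the plan sizes, so it is the one whose power the plan must deliver. The 26-per-arm case does not rescue the plan either: it assumes no dropout where the plan allows 20%, and three arms of 26 need 78 patients, not 54.

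A reader might infer two stronger claims that the documents do not support.
- That SNK will usually judge E vs C at 2.40. This depends on the P mean, which is not given; if P equals C or E it happens in only about half of trials.
- That the plan yields no effect estimate. Arm means and SDs are planned, so a point difference follows by subtraction. What is missing is a specified difference with its confidence interval.

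**Conclusion.** The mismatch is real and moderate. At the planned 21 evaluable per arm, SNK gives about 82-88% power for E vs C, against about 88-91% for a pre-specified contrast. If the stated 54 are split over three arms (18 each), the figures are about 75-82% against 83-86%.

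These results rest on the plan's own difference and SDs for E and C, and on assumed values for P. SNK is below the contrast in every scenario examined; only the size of the gap depends on P. The missing primary contrast and the missing interval do not depend on any assumption.

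The conflict between two groups, 54 patients and three arms is a related but separate matter. It also has to be resolved, because it decides which rows of the table apply.

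**What to change.** In the Statistical Analysis and Methods of Statistical Analysis sections, replace SNK for QoR-40 by ordered contrasts from the same ANOVA model, at one pre-specified primary postoperative day:

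1. E vs C at two-sided 0.05, with the mean difference and 95% CI.
2. E vs P at two-sided 0.05, only if step 1 is significant.
3. P vs C as an estimate with CI, not tested.

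Treat the other days and outcomes as secondary, reported as differences with CIs. Naming the day is essential: with days 1, 3 and 7 all open, E vs C first does not define one test, and the 5% family-wise error holds only within a single day.

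The cost is wording: no patients and no new data. The downside is that no claim on E vs P can be made if E vs C is not significant. If the sponsor prefers to keep SNK, the Sample Size Calculation section should restate the power for E vs C as about 82-88% at 21 evaluable per arm, with the values assumed for P.

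### Secondary outcomes have an efficacy role at P < 0.05 with no gate on QoR-40; with 10 tests and no true effect, a false result favouring TEAS has about an 8–20% chance, depending on the comparator

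*Combined protocol and SAP*

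**What the plan says.** The efficacy paragraph of Statistical Analysis (item 1c) gives QoR-40 its role: "we will treat the QoR-40 as the primary outcome to evaluate the efficacy of TEAS treatment". It then adds: "Additional four composite outcome measures (incidence of any postoperative complication, length of hospital stay, level of stress response, level of inflammatory response", and says that these "are also used as secondary outcomes to determine the efficacy of". In the text available for this review the sentence ends at that point.

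Outcome Measures shows what the four measures contain. For stress, "The Adrenocorticotropic Hormone (ACTH), Cortisol (COR) are chosen to address the level of perioperative stress response". Inflammation is represented by C-reactive protein (CRP) and the neutrophil-lymphocyte ratio (NLR). Blood is drawn at baseline and on postoperative days 1 and 3. Length of stay is one number per patient. For complications: "Assessment of incidence of postoperative complications will be going on three times and occur at postoperative day 1, 3, 7, respectively".

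Methods of Statistical Analysis applies one rule throughout: "All statistical tests are two-sided", and a P value below 0.05 "will be considered to be statistically significant". Quantitative variables go to one-way ANOVA with the SNK (Student-Newman-Keuls) method, and qualitative variables to a chi-square or Fisher's exact test.

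**The concern.** The four measures carry the label secondary, but the visible sentence gives them a part in deciding whether the treatment works. Three things that would normally limit that part are absent from the visible text:

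- a rule that a secondary claim needs a significant QoR-40 result first;
- any adjustment across outcomes or days (SNK deals only with group comparisons within one outcome at one time);
- a rule for combining or reconciling markers. The measures are called composite, but nothing says how ACTH and cortisol form one result, or what follows if they disagree or if day 1 and day 3 disagree.

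Nothing written therefore stops a trial that is negative on QoR-40 from claiming efficacy on one marker on one day. At stake is how secondary findings are interpreted. The error rate of the QoR-40 test is not affected.

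**Working it through.** **The plan's own figures.** The plan states no familywise error rate. Its sample size gives the arm sizes used below: (1.96 + 1.282)² × (11.1² + 13.7²) / 12.6² = 10.51 × 310.90 / 158.76 = 20.58, so 21 per group, as stated. The stated total of 54 over three arms is 54 / 3 = 18 per arm.

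**Counting tests** (from Outcome Measures; testing each marker on each day is an assumption)
- Stress: 2 markers × 2 postoperative days = 4
- Inflammation: 2 markers × 2 postoperative days = 4
- Length of stay: 1
- Complications: 1 if counted once per patient, 3 if tested at each assessment
- Total: 10, or 12

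**Any significant difference, independent tests, no true effect:** 1 − 0.95^k
- k = 4 (one test per domain): 18.5%
- k = 10: 40.1%
- k = 12: 46.0%

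**Allowing for correlation and direction.** The documents give no correlations, so these are assumed. Three-arm trials with 18 or 21 per arm were simulated with no true effect, using SNK for the nine quantitative tests and one complication test with an assumed 30% rate.

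| Assumed correlation (between outcomes / day 1 with day 3) | Any significant difference | E better than P or C | E better than C |
|---|---|---|---|
| 0 / 0 | 39–40% | 18–20% | 11–13% |
| 0.3 / 0.6 | 35% | 16–17% | 10–11% |
| 0.5 / 0.7 | 29–30% | 13–14% | 8–10% |

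**Hand check of the direction columns.** With no true effect, a significant SNK result always separates the highest and lowest of three arms. E is the best arm in 1/3 of such results, and E is best with C worst in 1/6. Treating the complication test alike, ten independent tests give approximate floors of 1 − (1 − 0.05/3)^10 = 15.5% for E better than P or C, and 1 − (1 − 0.05/6)^10 = 8.0% for E better than C. Results in which a second pair of arms also separates raise these to the simulated 18–20% and 11–13%.

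**Twelve tests.** Simulated any-difference rates were about 35–42% with moderate correlation and 29–32% with strong correlation. The direction split was not computed for this case.

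**Effect of a gate.** If secondary claims are allowed only after one pre-named QoR-40 comparison is significant at 0.05, the chance of any false secondary claim with no true effect cannot exceed the chance that the gate opens, which is 5%. If any of the three postoperative visits could open it, the bound would rise to 1 − 0.95³ = 14% for independent visits.

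**The case against.** The strongest reply is that roles are already ranked. QoR-40 is the primary outcome, the sample size rests on it alone, and the other measures are called secondary. The sentence that gives them an efficacy role is also incomplete in the available text, so its ending cannot be held against the plan. This stands in part: a ranking of roles is stated. But a ranking is not a testing rule, and the methods section, where such a rule would belong, supplies none.

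A second reply is that the number of tests is inferred. This also stands. The plan names four measures, and any postoperative complication reads naturally as one yes/no outcome. Assessment on three days is not a statement that three tests will be done. Separate marker tests are the likelier reading only because no combining rule is given.

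Three stronger readings are tempting, and the documents do not support them:

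- A reader might take 30–40% as the chance of a false claim that TEAS works. That figure counts any difference among three arms in either direction, including E worse than C, and P differing from C with E not involved.
- A reader might infer that the sponsor intends to declare success on a secondary outcome after a negative QoR-40 result. The text leaves this open but does not say it.
- A reader might infer that the primary test's error rate is inflated by the secondary tests. It is not.

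**Conclusion.** The point holds as a gap in the rules for interpreting secondary results. With 10 tests and no true effect, the chance of at least one significant difference of any kind is about 29–40%. The chance of a false result favouring TEAS is about 13–20% against P or C, and about 8–13% against C. If each domain is a single test, the any-difference chance is at most 18.5%.

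These figures rest on separate testing of each marker and day, assumed correlations, an assumed 30% complication rate and no effect on any outcome. The absence of a gate and of multiplicity control rests on the visible text. If the missing end of the sentence contains such a rule, the sponsor can point to it.

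**What to change.** Reword item 1c of Statistical Analysis so that the efficacy conclusion rests only on QoR-40, at one pre-named visit and for one pre-named group comparison. The plan currently lists postoperative days 1, 3 and 7 and three groups without choosing. Describe the secondary outcomes as supportive, reported as estimates with 95% CIs and with no stand-alone efficacy claim.

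If formal secondary claims are wanted, test them only after that QoR-40 comparison is significant. This limits any false secondary claim to at most 5% when there is no true effect. It does not protect the secondary outcomes once QoR-40 truly improves. For that, Holm across the four domains, with one pre-named marker and day for each laboratory domain, is an optional addition.

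The cost is SAP wording: no patients, visits or assays change. The downside is that fewer secondary results can be called significant.
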